8.3. Patient Re-Screening

Patients may repeat the Screening procedures to qualify for the study with approval from the medical monitor.

8.4. Patient Discontinuation and Termination

Patients have the right to discontinue study drug or withdraw from the study at any time for any reason, without prejudice to their medical care. Furthermore, the investigator may discontinue a patient from study drug. Consultation with the medical monitor should occur prior to study drug discontinuation or withdrawing a patient from the study. The reason for a patient's discontinuation from study drug or study termination will be recorded in the electronic case report form (eCRF).

8.4.1. Patient Discontinuation Criteria

Discontinuation refers to a patient's stopping administration of study drug. Reasons for study drug discontinuation may include the following:

- Confirmed clinical worsening event
- Occurrence of an AE or change in medical status that leads the investigator to be concerned about the patient's welfare
- Administrative reasons (*e.g.*, inability to continue)
- Sponsor termination of the study
- Voluntary withdrawal
- Females who become pregnant during the study
- Investigator unblinding

Patients must discontinue study drug if any of the following occur.

- ALT or AST > 8X ULN;
- ALT or AST > 5X ULN for 14 days;
- ALT or AST > 3X ULN and (total bilirubin > 2X ULN or INR > 1.5);
- ALT or AST > 3X ULN with the appearance of fatigue, nausea, vomiting, right upper quadrant pain or tenderness, fever, rash, and/or eosinophilia (> 5%);

Patients who are discontinued from study drug should still continue in the study, completing all study visits and undergo all scheduled study assessments, if possible.

8.4.2. Patient Termination Criteria

Termination refers to a patient's stopping study drug and all study assessments and visits. Reasons for study termination include the following:

- Loss to follow-up
- Death
- Withdrawal of consent

Every reasonable effort should be made to contact patients who do not return for a scheduled visit. The investigator should inquire about the reason for withdrawal, request the patient return all unused investigational product, request the patient return for end-of-treatment and follow-up visits (if applicable), and follow up with the patient regarding any unresolved AEs.

9. TREATMENT OF PATIENTS

9.1. Select Management Guidelines

The following guidelines apply to the management of study participants:

9.1.1. Management of Fluid Status

Specific risk mitigation procedures will be employed to reduce the potential for bardoxolone methyl-induced fluid overload. These procedures include exclusion of patients with any clinically significant renal disease, defined as an eGFR value of $< 45 \text{ mL/min/1.73 m}^2$. To exclude patients with significant cardiac dysfunction, the study will exclude patients with a history of left-sided heart disease. Patients who have evidence of volume overload at baseline, defined as BNP level of $> 400 \text{ pg/mL}$, will also be excluded. Laboratory data will also be used to monitor fluid status after randomization.

Additionally, after randomization patients will be closely monitored for rapid weight gain suggestive of fluid overload. Patients will be given a Sponsor-provided scale to use at home to collect and record their weights daily during the first 8 weeks of the treatment period and weekly thereafter. Patients who experience a five-pound (2.3 kilogram) or greater increase in weight since their Day 1 weight during the first 8 weeks of the study will be instructed to stop taking their study medication immediately and return to the clinic for an unscheduled physical examination and laboratory assessment by the investigator. Patients who experience a five pound (2.3 kilogram) or greater increase in weight between Day 1 and Week 8 may not restart their study medication until the investigator has completed and documented an assessment of fluid overload.

Patients who experience a five pound (2.3 kilogram) or greater increase in weight after the Week 8 study visit will be instructed return to the clinic for an unscheduled physical examination and laboratory assessment by the investigator. Study medication should not be discontinued unless the investigator has completed and documented an assessment of fluid overload and determines that the patient should be discontinued.

Investigators should advise patients to watch for signs and symptoms of fluid overload. Patients should be informed to notify their physicians immediately if they experience swollen feet, chest pain, shortness of breath with mild exertion or while lying down, or other relevant symptoms. The investigator should immediately assess symptoms of fluid overload and determine appropriate medical management, as necessary, including whether stopping drug administration is required. At the earliest sign of worsening or new onset peripheral edema or other signs and symptoms of acute volume overload, investigators will also be expected to determine if changes to a patient's diuretic regimen is needed.

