5.1.2. Fluid Overload

Similar to endothelin receptor antagonists (ERAs) in certain patient populations, including bosentan in advanced congestive heart failure and avosentan in advanced CKD, bardoxolone methyl treatment was found to be associated with an increased risk for fluid overload and heart failure hospitalizations in the BEACON trial, which enrolled patients with Stage 4 CKD (eGFR 15-29 mL/min/1.73 m²) and type 2 diabetes. The overall increased risk for fluid overload and heart failure events with bardoxolone methyl appeared to be limited to the first three to four weeks after initiation of treatment. Elevated BNP and prior hospitalization for heart failure were identified as risk factors that contributed to increased risk for these events. The increased risk for these events from bardoxolone methyl treatment had not been observed in six previous CKD studies, which were conducted mostly in patients with Stage 3b CKD (eGFR of 30-44 mL/min/1.73 m²), patients with hepatic dysfunction, cancer patients, or healthy volunteers.

Review of admission notes and narrative descriptions for heart failure hospitalizations in BEACON indicates that heart failure in bardoxolone methyl-treated patients was often preceded by rapid fluid weight gain (several kilograms within the first weeks of treatment initiation) and was not associated with acute renal decompensation or acutely reduced left ventricular contractility. Available data from BEACON and other studies suggest that bardoxolone methyl treatment can differentially affect hemodynamic status according to the clinical condition of patients and likely promotes fluid retention in patients with more advanced renal dysfunction and other recognized risk factors associated with heart failure at baseline.

In a Phase 2 dose-ranging study of the efficacy and safety of bardoxolone methyl in patients with pulmonary hypertension (LARIAT), risk mitigation procedures were employed to reduce the potential for bardoxolone methyl-induced fluid overload; these procedures excluded patients with the identified risk factors and ensured close monitoring for fluid retention within the first month of treatment. To date, the risk for acute fluid overload adverse events with bardoxolone methyl in late-stage CKD patients has not been observed in PAH patients.

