9.3.2. Permitted Medications

Allowed concomitant medications include the following:

- Antibiotics;
- Daily multivitamins or recommended daily supplements;
- Other medications intended to manage concurrent diseases, as authorized by the treating physician;
- Oral, implantable, or injectable contraceptives.

Patients taking medication chronically should be maintained on those same doses and dose schedules throughout the study period and should not have additions or changes made to their medications, as medically feasible.

The use of the following therapies, which may affect walking distance, are permitted during the study, provided the patients have been receiving a stable dosage for at least 30 days prior to Day 1. Unless medically indicated and discussed with the medical monitor, the doses of these agents should remain unchanged during the study.

- Vasodilators (including calcium channel blockers);
- Digoxin;
- L-Arginine supplementation;
- Diuretics;
- Agents to treat anemia (including but not limited to supplemental iron, erythropoietin, or intravenous iron);
 - If the patient receives intravenous iron therapy during Screening, the intravenous infusion must be performed at least 30 days prior to Day 1;
- Agents to treat neuropathic pain associated with peripheral neuropathy (such as pregabalin);
- Oxygen supplementation.

If receiving treatment for CTD with prednisone or any other drugs, the medications must remain the same for at least 90 days prior to Day 1. Doses for medications prescribed for the treatment

of CTD must remain stable for at least 30 days prior to Day 1 and for the duration of the study. PAH-specific background therapy should be taken as clinically indicated and prescribed by the physician for the duration of the study.

Refer to [Section 9.10.26](#) for guidelines on oxygen use during 6MWTs. Initiation of supplemental long-term oxygen therapy (oxygen application for more than 30 consecutive days) or persistent modification of a pre-existing supplemental long-term oxygen therapy (*i.e.*, need for a persistent increase of the amount of delivered oxygen for more than 30 days) due to worsening PAH is permitted.

Diuretics may be prescribed as clinically indicated throughout the study. Any changes to the doses of oxygen or diuretics throughout the course of the study must be recorded in the eCRF.

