8. STUDY DRUG AND OTHER MEDICATIONS

8.1. Prior and concomitant medications

All concomitant medications collected from screening through the end of the study will be classified by preferred terms according to the WHO Drug Dictionary (version 01MAR2016, type DDE+HD, format B2). Concomitant medications will be summarized by WHO Drug Dictionary classification. Special groups of medications (e.g. PAH, CTD) will be summarized by treatment group, by medical history as appropriate, and dose, if feasible.

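### The SAP's medication summary has no split at first dose and tabulates no diuretic starts or increases on treatment, so an excess on bardoxolone methyl would be diluted

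*Protocol*

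**What the plan says.** **The risk.** Protocol 5.1.2 reports that in the earlier trial in Stage 4 CKD "bardoxolone methyl treatment was found to be associated with an increased risk for fluid overload and heart failure hospitalizations". The excess appeared confined to the first three to four weeks. The same section says this risk had not, to date, been observed in PAH patients.

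**The response.** Protocol 9.1.1 asks investigators for a diuretic decision when early signs of fluid retention appear: "new onset peripheral edema or other signs and symptoms of acute volume overload, investigators will also be expected to determine if changes to" (diuretics are meant; the sentence is cut here). This is one of several responses. Patients who gain 2.3 kg or more in the first 8 weeks "will be instructed to stop taking their study medication immediately and return to the clinic for an unscheduled physical examination", and investigators must also judge whether drug should be stopped because of symptoms.

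**The data.** Protocol 9.3.2 states: "Any changes to the doses of oxygen or diuretics throughout the course of the study must be recorded in the eCRF". Diuretics and oxygen taken before the trial are "permitted during the study, provided the patients have been receiving a stable dosage for at least 30 days prior to Day 1", so each arm will contain some continuing users.

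**The analysis.** SAP 8.1 states: "All concomitant medications collected from screening through the end of the study will be classified by preferred terms". The summary is by WHO Drug Dictionary classification. PAH and CTD drugs are given as examples of special groups, to be shown by treatment group and, where feasible, by dose. SAP 12.1 lists concomitant medications as a safety variable but takes safety results from randomization, not from screening.

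**The concern.** A diuretic started for edema on Day 10 would count in the SAP 8.1 summary exactly as one taken unchanged since before screening. A dose increase in an existing user adds nothing to a count of users. The planned output therefore cannot show how many patients in each arm needed more diuretic after starting study drug, although the protocol has sites record it.

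Fluid overload is a prominent known risk of this drug, and the protocol builds specific mitigation around it. If investigators act early as asked, some of the difference between arms may appear as diuretic treatment rather than as heart failure events.

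The other readable outputs leave this gap open:

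- Home weights are not entered in the eCRF (Protocol 9.10.9).
- Clinic weight is summarized as values and changes from baseline (SAP 12.5). PAH patients on drug lost about 3 kg relative to placebo by Week 16 (Protocol 5.1.5), so mean weight can mask fluid gain in some patients.
- The readable adverse event plan (SAP 12.2) uses system organ class and preferred term, without a fluid-overload grouping or onset intervals.

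**Working it through.** The documents give no figure for diuretic use, so there is no planned number to reproduce. The calculation shows what an any-use table does to a difference in intensification.

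**Inputs**

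- 65 patients per arm (SAP Appendix B.2).
- b = share on a diuretic before first dose. Not given; taken as 20% to 70%.
- p = share with a diuretic started or increased after first dose, assumed equal in baseline users and non-users. Not given; taken as 15% on drug versus 5% on placebo, with 20% versus 5% as a second case.

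**Formula**

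A baseline user counts once whatever happens later, and a non-user counts only on starting. So:

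- any use = b + (1 − b) × p
- difference in any use = (1 − b) × (p on drug − p on placebo)

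The share of the excess kept is 1 − b, whatever the two rates are.

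**15% versus 5%** (true difference 10 points, true ratio 0.15 / 0.05 = 3.0)

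| b | Any use, drug | Any use, placebo | Difference (points) | Ratio |
|---|---|---|---|---|
| 20% | 0.20 + 0.80 × 0.15 = 32.0% | 0.20 + 0.80 × 0.05 = 24.0% | 8 | 1.33 |
| 30% | 0.30 + 0.70 × 0.15 = 40.5% | 0.30 + 0.70 × 0.05 = 33.5% | 7 | 1.21 |
| 50% | 0.50 + 0.50 × 0.15 = 57.5% | 0.50 + 0.50 × 0.05 = 52.5% | 5 | 1.10 |
| 70% | 0.70 + 0.30 × 0.15 = 74.5% | 0.70 + 0.30 × 0.05 = 71.5% | 3 | 1.04 |

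**Visibility.** The SAP plans no test here. Power serves only as a gauge of how readily a difference would be noticed. Exact power of a two-sided Fisher test at 0.05, 65 per arm:

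| Assumed rates | Intensification counted directly | Any use, b = 20% | b = 30% | b = 50% | b = 70% |
|---|---|---|---|---|---|
| 15% vs 5% | 37% | 13% | 10% | 6% | 4% |
| 20% vs 5% | 68% | 26% | 19% | 10% | 6% |

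Counting intensification directly is therefore no guarantee of detection at this sample size, but any-use counting lowers visibility in every case shown.

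**Window.** Starting at randomization (SAP 12.1) instead of screening (SAP 8.1) would not cure this. A continuing baseline user is still a user after randomization.

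**The case against.** The strongest reply is that the fluid signal does not depend on the medication table. New or worsening edema meets the protocol's definition of an adverse event (11.2.1.1), action taken is recorded (11.6), SAP 12.2 tabulates events by preferred term, clinic weight is summarized by arm and visit, and the DSMB reviews unblinded safety data quarterly (9.6.3). This stands as mitigation, but none of these outputs, as described, tabulates diuretic intensification by arm. It is also fair that PAH and CTD are only examples and that dose is mentioned where feasible: a diuretic group is unspecified, not excluded.

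A reader might infer more than the documents support:

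- **That an excess would nearly disappear.** This needs high baseline diuretic use, which the documents do not report. At b = 20%, four fifths of the excess remains.
- **That oxygen changes are also a response to fluid overload.** Protocol 9.1.1 does not name oxygen there. Section 9.3.2 refers to starting long-term oxygen or to a "need for a persistent increase of the amount of delivered oxygen for more than 30 days) due to worsening PAH is permitted".
- **That unseen oxygen changes cloud the 6MWD result.** Protocol 9.10.26 keeps the oxygen level set at screening for all later walk tests, and omits the test if that is no longer safe.
- **That a diuretic change is the first or only response.** Section 9.1.1 also provides for stopping study drug.
- **That a diuretic imbalance would confound the randomized comparison.** A change brought about by treatment is a consequence of treatment, not a baseline difference.

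**Conclusion.** The point holds as a gap in the safety tabulation. The protocol ties a diuretic review to early signs of volume overload and requires the changes to be recorded. The SAP states a summary window with no split at first dose, and its readable text specifies no table of later starts or increases. Under equal change rates in users and non-users, an any-use table keeps 1 − b of any excess. Dose increases in existing users are missed at any b above zero.

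The algebra is firm; the size is not. Both b and the intensification rates are assumptions, so the ratios and power figures are illustrations. Redacted SAP text could not be checked. The difference between the windows in SAP 8.1 and 12.1 is a separate, smaller inconsistency. This is a worthwhile low-cost improvement to the safety reporting and does not affect the primary efficacy analysis.

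**What to change.** 1. In SAP 8.1, separate medications ongoing and unchanged at first dose from changes made after first dose.
2. Add a descriptive table by arm of patients with a diuretic started or increased after first dose, by onset interval (first dose to Week 4, Weeks 4 to 8, after Week 8) and by baseline diuretic use. The first interval covers the period of excess risk described in Protocol 5.1.2.
3. Cross-reference the table from SAP 12.2 so that it is read beside the adverse events.
4. Reconcile the screening window in SAP 8.1 with the randomization window in SAP 12.1.
5. Optionally, tabulate oxygen starts or increases separately, labelled as a marker of worsening PAH.

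The cost is SAP wording and one or two tables from data the protocol already requires. The small downside is that dose changes must be derived from medication records. No test and no change to clinical management is needed.

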9.1.2. Management of Elevated Transaminase Levels (ALT and/or AST)

Nearly all instances of elevated transaminases are expected to be asymptomatic. Check transaminase levels (as well as total bilirubin (TBL), GGT, alkaline phosphatase (ALP), and International Normalized Ratio (INR)) within 48 to 72 hours during an unscheduled visit if the following occurs:

- ALT or AST levels > 3X ULN

Repeat testing every 72 to 96 hours until transaminase levels are below 3X the ULN for at least one week or until the patient withdraws consent.

Discontinue study drug administration permanently if any of the following occurs:

- ALT or AST > 8X ULN
- ALT or AST > 5X ULN for more than 2 weeks
- ALT or AST > 3X ULN and (TBL > 2X ULN or INR > 1.5)
- ALT or AST > 3X ULN with the appearance of fatigue, nausea, vomiting, right upper quadrant pain or tenderness, fever, rash, and/or eosinophilia (> 5%);

The hepatobiliary tree must be visualized (*e.g.*, ultrasound, MRI) and assessed if a patient discontinues taking study drug secondary to elevated transaminase levels. Additional tests/studies may be warranted depending on the clinical presentation.

9.1.3. Management of Muscle Spasms

Basic symptomatic relief is the first step in managing muscle spasm, including walking, adequate hydration, wearing socks, and stretching before bedtime. Assessment of levels of electrolytes such as magnesium, calcium and potassium may indicate the need for replacement. If vitamin D levels are low, supplementation may be warranted. Muscle relaxants may also help relieve symptoms.

9.1.4. Weight Loss

Ongoing assessments to ensure that the patient is receiving adequate nutrition and consideration of other etiologies of weight loss may be warranted for patients receiving bardoxolone methyl.

9.1.5. Hypomagnesaemia

In instances where a patient experiences hypomagnesaemia, defined as serum magnesium less than 1.3 mEq/L (0.65 mmol/L), consideration should be given to repletion of serum magnesium.

9.1.6. Nausea

Nausea may occur with higher doses of bardoxolone methyl. Nausea adverse events are typically mild and reversible within a few weeks after treatment initiation. If symptoms do not resolve, dose de-escalation, with consultation of the medical monitor, may be necessary.

9.1.7. Anemia

Anemia is a common occurrence in PAH patients. If a patient has serum levels of hemoglobin < 10.5 g/dL at Screening, the patient will be allowed to re-screen following anemia treatment. Re-screening can occur no sooner than 30 days following initiation of anemia treatment.

Patients with anemia who re-screen must repeat all Screening assessments at the re-screening. If the patient takes agents to treat anemia (including but not limited to supplemental iron, erythropoietin, or intravenous iron) the patient must remain on a stable dosage for at least 30 days prior to Day 1. If the patient receives intravenous iron therapy during Screening, the intravenous infusion must be performed at least 30 days prior to Day 1.

9.2. Description of Study Drug

Bardoxolone methyl (RTA 402) drug product information is shown in Table 4. Information about the placebo is shown in Table 5.

Table 4: Bardoxolone Methyl Drug Product Information

Description	Bardoxolone methyl capsule (2.5 mg, 5 mg)
[REDACTED]	[REDACTED]
Route of Administration	Oral

Table 5: Placebo Information

Description	Placebo for bardoxolone methyl capsule (2.5 mg, 5 mg)
Ingredients	Silicified Microcrystalline Cellulose Lactose monohydrate Magnesium Stearate Gelatin capsules Titanium Dioxide (capsule pigment)
Route of Administration	Oral

9.3. Concomitant Medications

9.3.1. Excluded Medications

Patients taking these medications or treatments will be ineligible for enrollment:

- Any other investigational drug or device as part of an interventional study;

- Intravenous or subcutaneous prostacyclin/prostacyclin analogue;
- Intravenous inotropes;
- Inhaled nitric oxide (excluding acute vasodilator testing during diagnostic cardiac catheterization);
- Prednisone at a dosage > 20 mg/day within 30 days prior to Day 1 or at any time during the study;

Patients who take excluded medications during the study should not discontinue study drug solely on this basis. Consultation with the medical monitor should occur prior to study drug discontinuation or withdrawing a patient from the study.

9.3.2. Permitted Medications

Allowed concomitant medications include the following:

- Antibiotics;
- Daily multivitamins or recommended daily supplements;
- Other medications intended to manage concurrent diseases, as authorized by the treating physician;
- Oral, implantable, or injectable contraceptives.

Patients taking medication chronically should be maintained on those same doses and dose schedules throughout the study period and should not have additions or changes made to their medications, as medically feasible.

The use of the following therapies, which may affect walking distance, are permitted during the study, provided the patients have been receiving a stable dosage for at least 30 days prior to Day 1. Unless medically indicated and discussed with the medical monitor, the doses of these agents should remain unchanged during the study.

- Vasodilators (including calcium channel blockers);
- Digoxin;
- L-Arginine supplementation;
- Diuretics;
- Agents to treat anemia (including but not limited to supplemental iron, erythropoietin, or intravenous iron);
 - If the patient receives intravenous iron therapy during Screening, the intravenous infusion must be performed at least 30 days prior to Day 1;
- Agents to treat neuropathic pain associated with peripheral neuropathy (such as pregabalin);
- Oxygen supplementation.

If receiving treatment for CTD with prednisone or any other drugs, the medications must remain the same for at least 90 days prior to Day 1. Doses for medications prescribed for the treatment

of CTD must remain stable for at least 30 days prior to Day 1 and for the duration of the study. PAH-specific background therapy should be taken as clinically indicated and prescribed by the physician for the duration of the study.

Refer to [Section 9.10.26](#) for guidelines on oxygen use during 6MWTs. Initiation of supplemental long-term oxygen therapy (oxygen application for more than 30 consecutive days) or persistent modification of a pre-existing supplemental long-term oxygen therapy (*i.e.*, need for a persistent increase of the amount of delivered oxygen for more than 30 days) due to worsening PAH is permitted.

Diuretics may be prescribed as clinically indicated throughout the study. Any changes to the doses of oxygen or diuretics throughout the course of the study must be recorded in the eCRF.

